#### ii. Exclusion

1.  $<18$  years of age
2. Renal dysfunction ( $\text{CrCl} < 30 \text{ ml/min}$ ) at any point during hospitalization while on enoxaparin
3. Pregnancy
4. Prisoners
5. Active bleeding
6. Already started on therapeutic enoxaparin and received  $>3$  consecutive doses
7. Therapeutic enoxaparin use within the last 3 months for  $>5$  consecutive days

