#### iii. Initial anti-Xa levels

1. Order levels 4 hours after at least three consecutive study doses of enoxaparin (will allow levels drawn between 3-5 hrs). If the level is not drawn, it will be reordered after the next dose.
2. Therapeutic anti-Xa: 0.5-1.1 IU/ml (GHS therapeutic range)
3. Adjustments will be made according to the dosing nomogram until a therapeutic level is obtained (see appendix). If a bleeding event occurs an anti-Xa level will be obtained.

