##### 2. Post intervention

- a. Scr, CrCl

- b. Initial dose of enoxaparin (mg/kg and mg)
  - c. Initial anti-Xa level and timing of level
  - d. Number of hours post dose
    - i. Level at 4 hours
    - ii. Level within range of 3-5 hours
  - e. Total number of doses received prior to level
- 3. Subsequent doses of enoxaparin (mg/kg and mg)
- 4. Subsequent anti-Xa levels after dosing adjustments
- 5. Time to first therapeutic anti-Xa level
- 6. Total days on enoxaparin
- 7. Bleeding events
  - a. Decrease in Hgb
  - b. Site of bleed
  - c. Blood product use
  - d. INR at onset of bleeding event for patients on warfarin
  - e. Additional anticoagulants and antiplatelets (date initiated and dose)
  - f. Platelet count at onset of bleeding event
  - g. Anti-Xa level at onset of bleeding event
  - h. PT and/or aPTT if available
- v. Respondent Burden-Total respondent burden will be minimal and depend on the time it takes to consent. Laboratory work would have to be done for this medication regardless of whether they were in the study or not.

e. Study Objectives/Outcomes

- i. Primary Objective
  - 1. To determine if enoxaparin dosing using 0.8mg/kg is more effective for achieving therapeutic steady state anti-Xa levels in morbidly obese patients when compared to 1 mg/kg dosing. (Morbid obesity is defined as a BMI > 40 kg/m^2)
- ii. Secondary Objectives
  - 1. To compare time to therapeutic anti-Xa levels for both dosing regimens
  - 2. To compare anti-Xa levels for both dosing regimens
  - 3. To compare number of dose adjustments required to achieve therapeutic anti-Xa levels using a dosing nomogram
  - 4. To validate dosing nomogram used to adjust low molecular weight heparin doses
  - 5. To evaluate major and minor bleeding events
- iii. Primary Outcome
  - 1. Proportion of patients with an initial therapeutic anti-Xa level at steady state in each group
    - a. Peak anti-Xa drawn 3-5 hours post dose after receiving at least 3 consecutive doses
- iv. Secondary Outcomes
  - 1. Time to therapeutic anti-Xa level for both groups
  - 2. Mean/Median therapeutic anti-Xa level for both groups
  - 3. Mean/Median number of dose adjustments required to achieve therapeutic anti-Xa level for both groups
  - 4. Proportion of patients with major and minor bleeding events (will follow until anti-Xa level is therapeutic)

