- a. Major bleed: Hgb drop of  $\geq 2\text{g/dL}$ , transfusion of 2 or more units of blood products, or retroperitoneal, intraocular, or intracranial hemorrhage
- b. Minor bleed: bleeding events not meeting major bleed criteria
- f. Risks to participation
  - i. Patients started on enoxaparin will be at risk for bleeding complications which is a known risk for this medication. Risk will be reduced by obtaining anti-Xa levels and adjusting the dose as needed. Other possible risks may be , anemia, decrease in platelets, elevation of liver enzymes, diarrhea, and nausea
- g. Benefits to subject or future benefits
  - i. By completing this study a strategy for dosing enoxaparin may be established for obese patients that is safer and allows for quicker therapeutic levels.
- h. Data analysis
  - i. Sample Size- In order to detect a 15% difference in the primary endpoint with a 2-sided significance level of 0.05, 50 patients per dosing group is needed to provide 80% power.
  - ii. Statistical Analysis
    - 1. Descriptive statistics will be used for all variables. Primary outcome will be analyzed using chi-square. Time to event will be analyzed using survival curves and log rank test. Medians will be compared using wilcoxon rank test.

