### 4. Plans for data management and monitoring

Safety data will be collected as mentioned above to monitor for adverse drug reactions, specifically bleeding. Patients with a decline in renal function that prompts a dose change will be excluded so that they may be put on a reduced dose listed in medication package insert.

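### Survival curves for time to a therapeutic anti-Xa level will overstate the share of randomised patients who became therapeutic if any leave study enoxaparin first; cumulative incidence would not

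*Combined protocol and SAP*

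**What the plan says.** Section 2.e.iv lists as its first secondary outcome "Time to therapeutic anti-Xa level for both groups". Section 2.h.ii gives the analysis in one sentence: "Time to event will be analyzed using survival curves and log rank test". No censoring rule, competing-event method or end of follow-up is stated for this outcome. The nearest statement, "will follow until anti-Xa level is therapeutic", is attached to the bleeding outcome.

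Other sections bear on who can reach the event:

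- Section 2.d.iii, on dosing: "Adjustments will be made according to the dosing nomogram until a therapeutic level is obtained".
- Section 2.a.ii makes creatinine clearance below 30 ml/min an exclusion "at any point during hospitalization while on enoxaparin", so it can apply after randomisation.
- Section 4: "Patients with a decline in renal function that prompts a dose change will be excluded".
- Section 2.d.iv records "Total days on enoxaparin", but no rule covers patients whose enoxaparin ends before a therapeutic level.

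No listed outcome counts the patients who never became therapeutic.

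**The concern.** The event is a therapeutic level on study enoxaparin. Once a patient is off study enoxaparin the event can no longer occur, so leaving is a competing event and not ordinary loss to follow-up.

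A survival curve has two ways to treat such a patient. If the patient is censored, the curve assumes that he or she would have come into range at the same rate as those who stayed. If the patient is dropped, he or she vanishes from the denominator. Both push one minus the curve above the share of randomised patients who got into range. Those who stay are titrated until they are in range, so the curve mostly describes the stayers.

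At stake is how the secondary result is read. Section 2.g names faster attainment of therapeutic levels as a possible benefit, and Section 1 gives a dosing and monitoring protocol as the ultimate goal. Readers will take the height of the curve as the share of patients brought into range.

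**Working it through.** **1. Inputs.** The documents give no figure for this analysis, so there is none to reproduce. They also give no exit rate; every exit rate below is an assumption.

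**2. An example with 50 patients in one arm (assumed counts).** Of the 50, 38 become therapeutic and 12 leave out of range. With leavers censored, 1−KM = 1 − ∏(1 − events/at risk). With leavers dropped, the denominator is 38. The true share has denominator 50.

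| Check | At risk | Therapeutic | Leave afterwards | 1−KM, leavers censored | Leavers dropped | True share |
|---|---|---|---|---|---|---|
| 1 | 50 | 23 | 7 | 23/50 = 46% | 23/38 = 61% | 23/50 = 46% |
| 2 | 20 | 10 | 4 | 1 − 0.54 × 10/20 = 73% | 33/38 = 87% | 33/50 = 66% |
| 3 | 6 | 4 | 1 | 1 − 0.27 × 2/6 = 91% | 37/38 = 97% | 37/50 = 74% |
| 4 | 1 | 1 | 0 | 100% | 38/38 = 100% | 38/50 = 76% |

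Censoring and dropping both overstate. Dropping does so from the first check.

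**3. Dependence on the exit rate.** Assume a share p is therapeutic at the first check and 50% of those still treated at each of four later checks. A fraction c of out-of-range patients leaves after each check. With r = 0.5(1 − c):

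- 1−KM, leavers censored = 1 − (1 − p) × 0.5⁴, which does not depend on c.
- True share = p + (1 − p)(r + r² + r³ + r⁴).

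For p = 45%, 1−KM = 1 − 0.55 × 0.0625 = 96.6%. With c = 10%, r = 0.45 and the true share is 0.45 + 0.55 × 0.7846 = 88.2%.

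| p | 1−KM at any c | True, c = 0 | c = 10% | c = 30% | c = 50% |
|---|---|---|---|---|---|
| 45% | 96.6% | 96.6% | 88.2% | 74.2% | 63.3% |
| 60% | 97.5% | 97.5% | 91.4% | 81.2% | 73.3% |

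With no exits the two agree.

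**4. Simulation with the Appendix A steps (400,000 patients per arm).**

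- From the documents: a mean level of 1.17 IU/ml at 1 mg/kg (the prospective study of hospitalised patients with BMI above 30, Section 1), the 0.5–1.1 IU/ml range, and the Appendix A dose changes.
- Assumed: lognormal levels with log-SD 0.35, dose-proportional; within-patient CV 15%; checks at 28 h and every 12 h after that, so the third is at 28 + 12 + 12 = 52 h; no carry-over; levels between 1.1 and 1.2 put in the 20%-decrease row; the hold above 2.0 not modelled; leavers censored; nobody leaves before the first check.

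At the first check about 49% (1 mg/kg) and 66% (0.8 mg/kg) are in range. The third-check curve shows 95% v 97% at every exit rate in the table. Overstatement is computed before rounding.

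| Leave after each check | True share, 1 v 0.8 mg/kg | Overstatement across the two arms |
|---|---|---|
| 2% | – | about 1 point |
| 5% | – | 2 to 3 points |
| 10% | 89% v 93% | 4 to 6 points |
| 20% | 83% v 90% | 8 to 12 points |

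**5. The log-rank test.** Take 50 per arm with equal chances of success at each check (45%, then 50%), and 50% v 10% leaving after each check. The log-rank test with leavers censored rejects in 5% of trials, its nominal level, although the true shares therapeutic are 63% v 88%. With leavers kept in the risk set, the rejection rate is 60%. The first test compares the rate of becoming therapeutic among those still treated; the second compares the share who got there. Both questions are legitimate, but they differ.

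**The case against.** The strongest case against is that the planned analysis does most of its job. The information in a time-to-range outcome lies early. Under the step 4 assumptions, the censored curve and the true share are identical at the first check, with the arms about 17 points apart. At the second check, with 10% exits, the gap is about 10 points on either. The log-rank test loses nothing: at 50 per arm it rejects in about 38% of trials in each exit scenario tried, against about 30% to 34% for a Gray-type comparison. All patients are inpatients with checks assumed 12 hours apart, so exits may be few. The outcome is secondary, and the primary chi-square already shows first-level failures by arm.

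Most of that stands, and it rules out several stronger readings that a reader might infer:

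- *Leavers will be censored.* No section says so. Section 4 says that renal-decline patients are excluded, which may mean dropped from the analysis. The rule is missing.
- *A bleed is an exit.* Section 2.d.iii says only "If a bleeding event occurs an anti-Xa level will be obtained". Nothing says that follow-up or treatment ends, so exits linked to the arm through bleeding cannot be assumed.
- *Both curves must reach 100%.* That holds only if the last patients at risk become therapeutic. If 40 of 50 are therapeutic and 10 are followed out of range to a common end, curve and true share are both 40/50 = 80%.
- *The log-rank test is invalid, or the curves hide the difference between arms.* The test is a valid cause-specific comparison. The gap shrinks only at later checks and higher exit rates (at 20% exits, third check: about 2 points shown, about 6 true).

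What remains is that the height of the curve is not the share of randomised patients who became therapeutic, and that nothing else in the listed outcomes reports that share. The promise in Section 2.h.ii of descriptive statistics for all variables does not commit the trial to it.

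**Conclusion.** The point holds as a fault in presentation and denominator for one secondary outcome. The plan foresees removal after randomisation, gives no rule for it, and names only a curve that overstates the share therapeutic whether leavers are censored or dropped. The direction is sure wherever anyone leaves out of range. The size is not, because the documents give no exit rates: at the third check it runs from about 1 point at 2% exits per check to 8 to 12 points at 20%.

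Those figures assume that leavers are censored and that nobody leaves before the first level. The zero at the first check depends on both: dropping leavers, or exits during the first study doses, would put an overstatement there too. The primary outcome and the validity of the log-rank test are not in question. The change is worth making before data are seen, because a rule for exits chosen afterwards is open to bias.

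**What to change.** Amend Section 2.h.ii for the first secondary outcome:

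1. Keep every randomised patient in the denominator, including those removed for renal decline, and state the end of follow-up.
2. Plot cumulative incidence (Aalen-Johansen) of the first therapeutic level by arm, with the end of study enoxaparin for any reason before a therapeutic level as the competing event. State whether the level that the Appendix A footnote calls for at creatinine clearance below 30 ml/min counts towards the outcome.
3. Report by arm the number and share who left never therapeutic.
4. Keep the log-rank test as the planned comparison, described as cause-specific. Gray's test is optional and not needed.

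The cost is analysis wording and one added field for the reason enoxaparin ended; days on enoxaparin and bleeding events are already collected. The curves will look slightly less favourable. If nobody leaves out of range, they are the same as those now planned.

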### d. Procedures

- i. Eligible patients will be approached while inpatient for written consent
- ii. Patients will be randomized in a 1:1 fashion into the 0.8mg/kg or 1 mg/kg group (using total body weight) stratified by BMI
  1. Doses will be rounded to the nearest 10mg due to graduations on syringe

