#### iv. Data Collection

##### 1. Baseline Data

- a. TBW, height, BMI
- b.  $BMI = TBW(\text{kg})/\text{height} (\text{m})^2$
- c. Age, Sex, Race
- d. Scr, CrCl (Cockcroft-Gault equation)
- e. Indication for treatment

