#### Appendix A. Dosing Nomogram for Adjusting Enoxaparin

Anti-factor Xa level (IU/mL)	Hold Next Dose	Dose Change	Repeat Anti-factor Xa*
<0.35	No	Increase by 25%	4h after next dose
0.35-0.49	No	Increase by 10%	4h after next dose
0.5-1.1	No	No	---
1.2-1.5	No	Decrease by 20%	4h after next dose
1.6-2.0	No	Decrease by 30%	4h after next dose
>2.0	Until level is 0.5 IU/mL	Decrease by 40%	4h after next dose

Adapted from CHEST 2001 and adjusted per institutional procedures

\*Will obtain level if CrCl<30 ml/min or bleeding event

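### The planned tests are valid but unadjusted; a prespecified model using the baseline creatinine clearance already collected would probably sharpen the anti-Xa level comparison at small cost

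*Combined protocol and SAP*

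**What the plan says.** Section 2.h.ii (Statistical Analysis) names one test per type of outcome. The in-range proportion is covered by "Primary outcome will be analyzed using chi-square". How long patients take to reach a therapeutic level is covered by "Time to event will be analyzed using survival curves and log rank test". The anti-Xa level and the number of dose adjustments fall under "Medians will be compared using wilcoxon rank test". The section names no covariate model and does not carry the stratification factor into the analysis, although section 2.d.ii says "Patients will be randomized in a 1:1 fashion into the 0.8mg/kg or 1 mg/kg group (using total body weight) stratified by BMI".

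Section 2.d.iv lists the baseline renal data as "Scr, CrCl (Cockcroft-Gault equation", without saying which body weight enters the equation. CrCl is recorded again after the intervention.

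Renal function appears in three rules:

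- The CrCl exclusion in section 2.a.ii applies "at any point during hospitalization while on enoxaparin".
- Section 4 says "Patients with a decline in renal function that prompts a dose change will be excluded".
- The footnote to Appendix A says "Will obtain level if CrCl<30 ml/min or bleeding event".

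Secondary objective 2 (section 2.e.ii) compares anti-Xa levels between regimens. The matching secondary outcome (section 2.e.iv) speaks of the therapeutic level, which leaves open whether out-of-range levels are included.

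**The concern.** The three renal rules only make sense if renal function affects how much drug effect a given dose produces. If baseline CrCl also predicts the anti-Xa level among enrolled patients, an unadjusted comparison leaves that variation in the error term, and chance differences in CrCl between arms go uncorrected. Randomisation is stratified by BMI only, so nothing in the design balances CrCl.

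What is at stake is mainly the precision of the level comparison. There is also a point of discipline: if CrCl turns out imbalanced, an adjustment chosen after seeing the data is less credible than one written down beforehand.

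**Working it through.** **1. The plan's own sample-size figure.** Section 2.h.i states 50 per group for a 15% difference, two-sided 0.05, 80% power, with no base rate. Taking 15% as absolute and using the 45% in-range rate that the Background reports for 1 mg/kg twice daily:

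n = [1.96·√(2·0.525·0.475) + 0.842·√(0.45·0.55 + 0.60·0.40)]² / 0.15² ≈ (1.384 + 0.588)² / 0.0225 ≈ 173 per arm.

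Fifty per arm gives about 32% power, so the stated figure is not reproduced from that rate. It is reached only near the extremes (0% vs 15%, or 85% vs 100%, gives 48 per arm). This is a separate matter, relevant here only because adjustment cannot repair it.

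**2. Precision of the level comparison.** Inputs: N = 100 (section 2.h.i); r, the correlation of baseline CrCl with log anti-Xa, is assumed. The variance of the adjusted arm difference relative to the unadjusted one is

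(1 - r²) × [1 + 1/(N - 4)] = (1 - r²) × 1.0104.

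| Assumed r | Variance ratio | Equivalent N | Power, if 80% unadjusted |
|---|---|---|---|
| 0 | 1.010 | 99.0 | 79.6% |
| 0.1 | 1.000 | 100.0 | 80.0% |
| 0.2 | 0.970 | 103.1 | 81.2% |
| 0.3 | 0.920 | 108.8 | 83.2% |
| 0.4 | 0.849 | 117.8 | 86.0% |
| 0.5 | 0.758 | 132.0 | 89.6% |

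Break-even is at |r| of about 0.10.

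**3. Chance imbalance.** The standardised CrCl difference between arms has SD √(2/50) = 0.20, so 95% of trials fall within ±0.39 SD. P(|difference| > 0.3 SD) = P(|Z| > 1.5) = 0.134. Assume CrCl explains 20% of the variance of log anti-Xa (r = √0.2 = 0.447) and a log-SD of 0.40. A 0.3 SD imbalance then shifts the difference in mean log level by 0.3 × 0.447 × 0.40 = 0.054. If levels are proportional to dose, the dose effect is ln(0.8) = -0.223, so the shift is 0.054/0.223 = 24% of it. The unadjusted standard error is 0.40 × 0.20 = 0.08, so the same shift is 0.054/0.08 = 0.67 of a standard error. It can go in either direction.

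**4. Primary outcome.** The target range is a two-sided band, 0.5-1.1 IU/ml (section 2.d.iii), so CrCl can move a patient in or out at either end. Simulation used 50 per arm, log-normal levels proportional to dose, 1 mg/kg mean 0.9-1.17 IU/ml and coefficient of variation 0.30-0.45 (assumed). The variance ratio for the adjusted risk difference was 0.96-1.01 at r = 0.3 and 0.88-1.01 at r = 0.5. With log-SD 0.40 and the 0.054 shift divided between arms, the in-range difference moves 3.4 points if the 1 mg/kg mean is 1.17 (standard error 9.8 points), about 1.5 points if it is 1.0, and 0.03 points if it is 0.9.

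**5. Validity of the planned test.** Under a simulated null (r = 0.3, coefficient of variation 0.40), type I error at nominal 5% was 4.3% for Wilcoxon and 4.6% for the adjusted regression.

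**The case against.** The strongest reply is that nothing planned is wrong. Chi-square, log-rank and Wilcoxon are valid under randomisation, and chance imbalance in CrCl is already part of the sampling error they allow for. Lost precision and uncorrected imbalance are therefore largely one issue, not two. This stands. A reader might infer that the planned comparisons are biased or have inflated type I error; neither the documents nor the simulation supports that.

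Second, the link to exposure is inferred. The rules act on a threshold of 30 ml/min or on a decline that changes the dose. The documents do not say that CrCl drives anti-Xa among patients above that threshold, the exclusions narrow the range, and no correlation or anti-Xa SD is given. This also stands, so the gain must be shown over a range that includes zero. The inference is still reasonable: apart from body size, already in the dose and the stratification, no other characteristic collected at baseline is tied to exposure in this way.

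Third, it is tempting to say that adjustment is free and removes renal imbalance. It costs one or two degrees of freedom and requires a choice of scale and functional form. It puts a model-based geometric mean ratio beside the comparison of medians, and it corrects only the modelled, baseline part of any imbalance. With the weight undefined in a BMI ≥40 population, CrCl is an ambiguous covariate until the plan fixes it.

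Finally, if the secondary outcome means only levels already in range, the sample is selected after randomisation and the gains in the table do not apply.

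**Conclusion.** The point holds as an improvement to the secondary level comparison. At 50 per arm the variance change runs from about +1% (r = 0) to -8% (r = 0.3) and -24% (r = 0.5). The possible loss is small and the possible gain useful. All of this rests on an assumed r, on a roughly linear relation on the log scale, and on analysing all initial levels.

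A reader might infer that the primary analysis should be replaced, or that adjustment would rescue its power. The expected gain for the in-range proportion is small or nil. Even an effective size of 55 to 67 per arm would give only about 35% to 41% power for 45% vs 60%. Nor does a baseline covariate deal with patients removed after randomisation for renal decline, who could unbalance the arms by another route.

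**What to change.** In section 2.h.ii:

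- **Level comparison.** State that the initial steady-state anti-Xa level, for all patients with an initial level and not only those in range, is compared by linear regression of log level on arm, BMI stratum and log baseline CrCl. Report the geometric mean ratio with 95% CI, and keep Wilcoxon as the unadjusted supporting test.
- **Covariate definition.** State which body weight enters Cockcroft-Gault, that the baseline and not the post-intervention value is used, and how a missing baseline value is handled.
- **Primary outcome.** Keep chi-square as the primary test. Label any CrCl-adjusted standardised risk difference as supportive only.
- **Outcome wording.** Align secondary outcome 2 in section 2.e.iv with secondary objective 2, so that it is clear all initial levels count.

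The cost is a few lines of text and code, with no new data collection. In variance terms it is about 1% if CrCl is not prognostic. With two added terms (CrCl and a two-level BMI stratum, the number of strata being an assumption) the factor is 1 + 2/95 = 1.021 if neither is prognostic; this is an upper figure, because stratification keeps BMI near balance. Post-randomisation renal exclusions and the sample-size basis need their own changes.
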